7.2 Endpoints

Primary endpoints*

- 1) Change in seizure frequency

The definition of a “responder” is a patient with a $\geq 50\%$ reduction in seizure frequency.

Secondary endpoints

Clinical factors predictive of immunotherapy response.

The following clinical factors will be analyzed with respect to prediction/correlation with favorable outcome.

- 1) Interval from symptom onset to immunotherapy treatment
- 2) Type of onset
- 2) Clinical course
- 3) Seizure type and frequency
- 4) EEG abnormalities
- 5) Presence of other neurological symptoms or signs (tremor, headache, myoclonus)
- 6) CSF findings (White cell count; protein)
- 7) Neural autoantibody type (LGI1, CASPR2, other) and titer (blood draws will be performed at baseline, 6 weeks and 12 weeks (for placebo group only)
- 8) Change in The Repeatable Battery for the Assessment of Neuropsychological Status (RBANS) scale scores

Tertiary endpoints

For the 1 year follow up “observational study”

- “Responder” patients from Trial will be randomly assigned to 2 clinical groups:
 - Immunotherapy (as per physician/insurance approval): mycophenolate mofetil 2000mg daily or azathioprine 2mg/kg +/- IVIG taper or IVMP taper
 - No immunotherapy
- Subjects will be followed for relapse for a total of 12 months (see study schedule of events).
- Patients will keep a daily seizure diary and record any adverse events while on immunotherapy.
- The study coordinator will call patients every month review seizure history and adverse events.
- Patients will be seen at 6 months and 12 months as part of standard clinical care-neurological examination will be recorded.
- Relapse will be defined as $\geq 20\%$ increase in seizure frequency compared with post IVIG frequency.
- Cognition will be assessed by the study coordinator who will perform Telephone Interview for Cognitive Status and the KOKMEN at each monthly call.
- If relapse occurs, the patient will be seen at the clinic. Patients on no therapy will be started on immunotherapy, those on therapy will have treatment adjusted as per current standard clinical care.

8 Safety and Adverse Events

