- Multiple seizure types or Faciobrachial dystonic seizures
- AED Resistance
- Personal or family history (1st degree relative) of autoimmunity
- History of recent or past Neoplasia
- Evidence of CNS inflammation on CSF (elevated protein, pleocytosis, oligoclonal bands, + CSF index)
- Evidence of CNS inflammation on MRI (mesial temporal or other regional T2 hyperintensity)
- Hypometabolism/hypermotabolism on functional/PET imaging
- Detection of neural autoantibody

IVIg in autoimmune epilepsy: Autoimmune epilepsy is increasingly recognized in the spectrum of neurological disorders characterized by detection of neural autoantibodies in serum or spinal fluid and responsiveness to immunotherapy. We recently performed a retrospective review of 29 patients treated with 6-12 weeks of intravenous methylprednisolone or immune globulin, or both (the current standard immunotherapy trial protocol used at Mayo Clinic), for suspected autoimmune epilepsy.⁹ Similar to AED trials, treated patients were considered “responders” if there was a 50% or greater reduction in seizure frequency. A total of 18 patients (62%) responded favorably to the immunotherapy trial (Figure 2). Ten of these (56%) achieved seizure freedom and the remainder had more than 50% reduction in seizure frequency. Five of eleven responders with daily seizures (45%) became seizure free after completion of the immunotherapy trial, 45% had only monthly seizures and 1/11 (9%) had weekly seizures. Two out of 4 responders with weekly seizures (50%) became seizure free and the other two had monthly seizures. All three responders with monthly seizures became seizure free. None of the responders who had generalized tonic-clonic seizures at presentation (8/18; 44%) continued having these after completion of the trial. Fifteen patients (52%) responded to the first agent tried and 14 (48%) did not. Having failed the first agent, 3 of 7 patients (43%) responded to a second agent (Figure 2). Of the fifteen patients who improved with the first immunotherapy trial, 6 responded within the first week, 6 responded in the second to fourth weeks and one required treatment for 5 weeks before improvement was noted.

Figure 2. Flow-chart of "immunotherapy trial" and response according to antibody type.

[figure not shown]

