3.3 Primary Study Endpoints

Reduction of 50% or more, in seizure frequency with IVIG treatment.

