7.1 Statistical Methods

Dr. [REDACTED], senior statistician and Professor of Biostatistics, will be responsible for analyzing study data. The treatment (IVIg or placebo) will be unblinded at the 6 week follow up.

Randomized Placebo Controlled Trial:

The study will include 30 patients (15 per arm). Data collected will be summarized using descriptive statistics such as mean, standard deviation, median, minimum and maximum for continuous variables and using frequencies and percentages for categorical variables (see Study Endpoints). Primary outcome, which is binary variable, i.e. proportion of patients responding to treatment (yes, no) will be estimated along with 95% exact binomial confidence intervals for each arm of the respective study. These proportions will then be compared using Fisher's exact test within the study. Continuous outcomes of interest will be compared using two sample t-test or Wilcoxon rank sum test as appropriate.

Multiplicity

Due to smaller sample sizes, no adjustment for multiple comparisons is done.

Power/Sample Size

Sample size and power calculations for various scenarios using Nquery advisor software version 7.0 are provided below.

VGKC complex antibody positive

Based on preliminary data, assuming 70% responders on IVIG vs. 10% on Placebo, a total sample size of 30 (i.e.15 per group) will have 89% power at an alpha level of 5% using Fisher's exact test.

Dropouts

If we assume a maximum dropout rate of 20%, we would still maintain >80% power. In an event if the dropout rate exceeds anticipated rate, we would still have 82% power to detect hypothesized difference (70% versus 10%) with as few as 12 patients per group.

Effect of patient enrolment on power analysis in Randomized Placebo Controlled Trial

Group 1: Assuming the rate of positive response to IVIG and placebo is 70% and 10%, respectively:

Two group Fisher's-exact test of equal proportions (odds ratio = 1) (equal n's)

	1	2	3	4
Power (%)	82	89	94	97
n per group	12	15	17	19

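### Section 7.2 labels the primary endpoint as a change in seizure frequency while the rest of the plan uses the binary responder; name the responder as primary and put any continuous analysis on a proportional, baseline-adjusted scale

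*Combined protocol and SAP*

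**What the plan says.** - Section 7.2, under its primary endpoints heading, numbers one item, "Change in seizure frequency". The line below defines a responder as a patient whose seizure frequency falls by at least 50%. It does not say that the responder proportion is the endpoint.
- Section 3.3 gives the primary endpoint as "Reduction of 50% or more, in seizure frequency with IVIG treatment".
- Section 7.1 describes the "Primary outcome, which is binary variable, i.e. proportion of patients responding to treatment (yes, no"), and adds: "These proportions will then be compared using Fisher's exact test within the study".
- The power statement in 7.1 rests on the same outcome: "assuming 70% responders on IVIG vs. 10% on Placebo", for which "a total sample size of 30 (i.e.15 per group) will have 89% power at an alpha level of 5% using Fisher's exact test".
- For continuous data, 7.1 has one rule: "Continuous outcomes of interest will be compared using two sample t-test or Wilcoxon rank sum test as appropriate". It does not list the outcomes covered, give a scale for change (absolute, percent or log), or mention a baseline covariate.
- Section 4.1 admits patients from 2 seizures a week upward with no upper limit. Section 4.3 asks for at least one week of diary before the first evaluation. No mean, SD or distribution of baseline frequency is given.

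**The concern.** There are two linked gaps. First, the label in 7.2 is a change measure, while 7.1 calls the primary outcome binary. The endpoint section and the methods section should carry the same name for the primary.

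Second, if change in frequency is also analysed as a continuous quantity, the plan leaves open the scale, the choice between two tests and any baseline adjustment. Scale matters in this population. Entry has no ceiling, and the retrospective series in section 1.1 included many patients with daily seizures ("Five of eleven responders with daily seizures (45%) became seizure free after completion of the immunotherapy trial"; 11 of the 18 responders). On an absolute scale, a fall from 40 to 30 a week counts for more than a fall from 4 to 0, although the first patient is a non-responder and the second is seizure free. The trial's aim and its responder rule are both proportional. An absolute-change analysis could therefore look null beside a clearly positive responder result, and readers would have to explain a disagreement produced by the choice of scale.

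**Working it through.** **1. The plan's own figure.** Inputs from 7.1: n = 15 per arm, 70% v 10%, alpha 5%. Power is the sum over a, b = 0..n of Bin(a; n, 0.70) × Bin(b; n, 0.10), taken over the tables where the two-sided Fisher p-value is at most 0.05.

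| n per arm | Computed | Stated |
|---|---|---|
| 12 | 0.826 | 82% |
| 15 | 0.894 | 89% |
| 17 | 0.948 | 94% |
| 19 | 0.975 | 97% |

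The stated power reproduces, and it belongs to the responder analysis. Nothing below changes it.

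**2. How each scale scores a patient.** Here b is the baseline and y the on-treatment weekly rate.

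| b to y | y − b | 100(y − b)/b | log((y+0.5)/(b+0.5)) |
|---|---|---|---|
| 40 to 30 | −10 | −25% | log(30.5/40.5) = −0.28 |
| 4 to 0 | −4 | −100% | log(0.5/4.5) = −2.20 |
| 40 to 4 | −36 | −90% | log(4.5/40.5) = −2.20 |

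The absolute scale reverses the clinical order of the first two rows. The percent and log scales do not.

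**3. Power of the continuous analyses.** The documents give no baseline distribution, so the following are assumptions:

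- 15 per arm; 70% v 10% responders (from 7.1).
- Lognormal baseline with a floor of 2: median 7 with log-SD 0.8, or median 10 or 14 with log-SD 1.2. Before the floor, the 95th percentile runs from 7 × exp(1.645 × 0.8) = 26 to 14 × exp(1.645 × 1.2) = 101 a week.
- A responder is seizure free with probability 10/18 (the retrospective series in 1.1); otherwise y/b is uniform on 0.05-0.5.
- A non-responder's y/b is lognormal around 1 (SD 0.25), restricted to above 0.5.

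Simulated power, two-sided 5%, no count noise:

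| Analysis | Power |
|---|---|
| Responder, Fisher | 89-90% |
| Absolute change, t-test | 43-66% |
| Absolute change, Wilcoxon | 71-78% |
| Percent change, t-test | 89-91% |
| Percent change, Wilcoxon | 83-85% |
| Log ratio t-test, or log rate adjusted for baseline | 84-89% |

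With assumed Poisson count noise added, the log-scale analyses hold at 84-86%, while the percent-change t-test falls to 75-81%.

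**4. Sensitivity to the assumed baseline spread.** A second model used a continuous log-ratio (SD 0.6 or 1.0), baseline median 5 or 14, and log-SD from 0.3 to 1.6. Power relative to the log-ratio t-test at 70% v 10%:

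- Absolute-change t-test: 0.93-0.98 at log-SD 0.3 (with log-ratio SD 0.6), 0.71-0.79 at log-SD 1.0, and 0.46-0.57 at log-SD 1.6.
- Absolute-change Wilcoxon: 0.85-0.99 throughout.

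With a weaker assumed effect (about 50% v 15%), the absolute-change t-test kept 0.74 down to 0.34 and the Wilcoxon 0.84-0.90. Under the null, each test taken singly stayed at or below 5%.

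**The case against.** The best defence is that the primary is clear in substance. The responder definition stands directly under the 7.2 label; 3.2, 3.3, 5.2, the Study Summary and 7.1 all use the responder criterion or its proportion; and every power figure is for Fisher's test. A reader might infer that 7.1 and 7.2 set up two rival primaries, either of which could be presented as the trial's answer. The documents do not support that: 7.1 says outright that the primary outcome is binary and names its test. The plural heading is weak evidence of a second efficacy primary, since one item is numbered and 3.5 places safety among the primary endpoints.

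A reader might also infer that the plan prescribes an absolute-change comparison and so gives up half its power. It names tests and not a scale, and the seizure changes it does define (50% reduction, 50% increase, 20% increase for relapse) are all relative. On percent change, without count noise, the plan's own t-test does as well as the log ratio. A loss of about half belongs only to an absolute-change t-test under a wide assumed baseline spread. For skewed data, the wording of 7.1 could well lead to Wilcoxon, which loses much less.

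Two further objections stand. The 10/18 and 11/18 come from mixed antibody types treated with methylprednisolone, IVIG or both, not from this trial's population on IVIG alone. And the log ratio has a weakness of its own: with the 0.5 constant, 4 to 0 scores the same as 40 to 4, and among seizure-free patients the score depends only on baseline (2 to 0 gives log(0.5/2.5) = −1.61; 40 to 0 gives log(0.5/40.5) = −4.39).

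What the defence does not supply is a stated scale or baseline adjustment, or a label in 7.2 that matches 7.1.

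**Conclusion.** The point holds as a mismatch of labels plus an underspecified supportive analysis. The mismatch between 7.2 and 7.1/3.3 is a fact of the text; the binary endpoint is probably the one intended, and its 89% power stands.

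The size of the second part is conditional. If change in frequency is analysed as an absolute difference, power under the assumed skewed baselines is about 43-66% by t-test and 71-78% by Wilcoxon, against 84-89% on a log scale. The loss shrinks to a few per cent if the baseline spread is narrow, and largely disappears if percent change is used and count noise is small.

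A reader might also fear serious false-positive inflation from choosing among analyses. With identical arms, claiming the best of the responder test, the absolute-change t-test and the absolute-change Wilcoxon rejects in about 5-7% of simulated trials, so the effect is modest. The main cost is power and a continuous result that is hard to interpret, not the validity of the primary test.

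**What to change.** - In 7.2, name the between-arm comparison of responder proportions, as in 3.3 and 7.1, as the single primary efficacy endpoint.
- List change in seizure frequency as a supportive endpoint. State the baseline and on-treatment diary windows from which the weekly rates b and y are taken.
- Analyse it on a proportional scale with baseline adjustment: for example, log((y+0.5)/(b+0.5)) regressed on arm, with log baseline rate as covariate. Report the exponentiated arm difference as a between-arm rate ratio with a 95% interval.
- In 7.1, exclude absolute change in seizure frequency from the general t-test/Wilcoxon rule.
- Because results for seizure-free patients depend on the added constant, prespecify a sensitivity check such as a Wilcoxon test on percent change.

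The cost is a few lines in 7.1 and 7.2. The diary data are already collected, and neither the sample size nor the primary test changes.

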8.1 Definitions

Unanticipated Problems Involving Risk to Subjects or Others (UPIRTSO)

Any unanticipated problem or adverse event that meets the following three criteria:

- Serious: Serious problems or events that results in significant harm, (which may be physical, psychological, financial, social, economic, or legal) or increased risk for the subject or others (including individuals who are not research subjects). These include: (1) death; (2) life threatening adverse experience; (3) hospitalization - inpatient, new, or prolonged; (4) disability/incapacity - persistent or significant; (5) birth defect/anomaly; (6) breach of confidentiality and (7) other problems, events, or new information (i.e. publications, DSMB reports, interim findings, product labeling change) that in the opinion of the local investigator may adversely affect the rights, safety, or welfare of the subjects or others, or substantially compromise the research data, **AND**
- Unanticipated: (i.e. unexpected) problems or events are those that are not already described as potential risks in the protocol, consent document, not listed in the Investigator's Brochure, or not part of an underlying disease. A problem or event is "unanticipated" when it was unforeseeable at the time of its occurrence. A problem or event is "unanticipated" when it occurs at an increased frequency or at an increased severity than expected, **AND**
- Related: A problem or event is "related" if it is possibly related to the research procedures.

Adverse Event

An untoward or undesirable experience associated with the use of a medical product (i.e. drug, device, biologic) in a patient or research subject.

Serious Adverse Event

Adverse events are classified as serious or non-serious. Serious problems/events can be well defined and include;

- death
- life threatening adverse experience
- hospitalization
- inpatient, new, or prolonged; disability/incapacity
- persistent or significant birth defect/anomaly

and/or per protocol may be problems/events that in the opinion of the sponsor-investigator may have adversely affected the rights, safety, or welfare of the subjects or others, or substantially compromised the research data.

All adverse events that do not meet any of the criteria for serious, should be regarded as **non-serious adverse events**.

Adverse Event Reporting Period

For this study, the study treatment follow-up period is defined as (7) days following the last administration of study treatment. The study period during which adverse events must be reported is defined as the period from the initiation of any study procedures to the end of the study treatment follow-up.

Preexisting Condition

A preexisting condition is one that is present at the start of the study. A preexisting condition should be recorded as an adverse event if the frequency, intensity, or the character of the condition worsens during the study period.

General Physical Examination Findings

At screening, any clinically significant abnormality should be recorded as a preexisting condition. At the end of the study, any new clinically significant findings/abnormalities that meet the definition of an adverse event must also be recorded and documented as an adverse event.

Post-study Adverse Event

All unresolved adverse events should be followed by the sponsor-investigator until the events are resolved, the subject is lost to follow-up, or the adverse event is otherwise explained. At the last scheduled visit, the sponsor-investigator should instruct each subject to report, to the sponsor-investigator, any subsequent event(s) that the subject, or the subject's personal physician, believes might reasonably be related to participation in this study.

Hospitalization, Prolonged Hospitalization or Surgery

Any adverse event that results in hospitalization or prolonged hospitalization should be documented and reported as a serious adverse event unless specifically instructed otherwise in this protocol. Any condition responsible for surgery should be documented as an adverse event if the condition meets the criteria for an adverse event.

Neither the condition, hospitalization, prolonged hospitalization, nor surgery are reported as an adverse event in the following circumstances:

- Hospitalization or prolonged hospitalization for diagnostic or elective surgical procedures for a preexisting condition. Surgery should **not** be reported as an outcome of an adverse event if the purpose of the surgery was elective or diagnostic and the outcome was uneventful.
- Hospitalization or prolonged hospitalization for therapy of the target disease of the study, unless it is a worsening or increase in frequency of hospital admissions as judged by the clinical investigator.

8.2 Recording of Adverse Events

At each contact with the subject, the study team must seek information on adverse events by specific questioning and, as appropriate, by examination. Information on all adverse events should be recorded immediately in the source document, and also in the appropriate adverse event section of the case report form (CRF) and Adverse Event Report Form. All clearly related signs, symptoms, and abnormal diagnostic, laboratory or procedure results should be recorded in the source document.

All adverse events occurring during the study period must be recorded. The clinical course of each event should be followed until resolution, stabilization, or until it has been ultimately determined that the study treatment or participation is not the probable cause. Serious adverse events that are still ongoing at the end of the study period must be followed up, to determine the final outcome. Any serious adverse event that occurs after the study period and is considered to be at least possibly related to the study treatment or study participation should be recorded and reported immediately.

8.3 Reporting of Serious Adverse Events and Unanticipated Problems

When an adverse event has been identified, the study team will take appropriate action necessary to protect the study participant and then complete the Study Adverse Event Worksheet and log. The sponsor-investigator will evaluate the event and determine the necessary follow-up and reporting required.

8.3.1 Sponsor-Investigator reporting: notifying the Mayo IRB

The sponsor-investigator will report to the Mayo IRB any UPIRTSOs and Non-UPIRTSOs according to the Mayo IRB Policy and Procedures.

Reminder: According to Mayo IRB Policy any serious adverse event (SAE) which the Principal Investigator has determined to be a UPIRTSO must be reported to the Mayo IRB as soon as possible but no later than 5 working days after the investigator first learns of the problem/event.

The following information will be collected for documentation of adverse events.

Information collected on the adverse event worksheet (*and entered in the research database*):

- Subject's name:
- Medical record number:
- Disease/histology (if applicable):
- The date the adverse event occurred:
- Description of the adverse event:
- Relationship of the adverse event to the research (drug, procedure, or intervention):
- If the adverse event was expected:
- The severity of the adverse event: (use a table to define severity scale 1-5)
- If any intervention was necessary:
- Resolution: (was the incident resolved spontaneously, or after discontinuing treatment)
- Date of Resolution:

The sponsor-investigator will review all adverse event reports to determine if specific reports need to be made to the IRB and FDA. The sponsor-investigator will sign and date the adverse event report when it is reviewed. For this protocol, only directly related SAEs/UPIRTSOs will be reported to the IRB.

8.4 Unmasking/Unblinding Procedures

While the safety of the subject always comes first, it is still important to seriously consider if unmasking/unblinding the study therapy is necessary to ensure a subject's safety.

- The need for unmasking/unblinding of study therapy on a subject will be determined by the PI
- Documentation of Unmasking/unblinding will be in the subject's source document.
- In most cases, the unmasking/unblinding will be part of managing an SAE, and will be reported with the SAE.
- However, in cases where unmasking/unblinding was not associated with an SAE, such actions should be reported in a timely manner (7 days). While there is no regulation governing this timeline, it is suggested to use the same timeline requirements for reporting of SAEs.

